We will investigate the percentage of patients with 90% complete core variables in ISAR over time. The completeness of individual core variables will also be investigated, as well as

the proportion of individuals that meet criteria for $\geq 90\%$ completeness of core variables. There are 38 core variables in the ISAR, as voted for in the Delphi 2017 exercise. These are shown in **Appendix 1** (Section 13.1) along with some more information about the ISAR schedules. We will also investigate patient characteristics associated with completeness of data for targeted strategies.

Objective 3: Differential characteristics and proportion of patients on LTOCS in the ISAR registry over time

Outcome: Proportion of patients on LTOCS (at visit)

Exposure: Time (calendar year and pre-specified periods of change)

Covariates: Age, gender, country, country-specific factors

The characteristics of patients in the ISAR registry who are prescribed LTOCS are likely to change with policy initiatives, awareness of serious adverse events, increased knowledge about asthma among participating sites, and biologic availability. ISAR may also have prompted behaviour change among clinicians who treat patients with severe asthma thereby affecting their treatments and/or outcomes. We will assess trends in LTOCS use over time, adjusting for age and gender, and stratifying by country and country-specific factors (e.g. participation in ISAR consortium, data capture system). We will also evaluate proportion and time to stopping/reducing the dose ($\leq 5\text{mg}$) of LTOCS to assess differences in clinical practice over calendar time.

Objective 4: Severity of asthma in those initiating biologic treatment over time

Outcome: Initiation of biologic treatment by asthma severity indicator

Exposure: Time (calendar year and pre-specified periods of change)

Covariates: Age, gender, country-specific factors

We will investigate and describe initiation of first biologic treatment by asthma severity indicator over calendar time, also adjusted for age and gender. We will further explore whether this changes as quality of data improves and/or in response to key practice change initiatives (quality improvement, seminal papers). Asthma severity indicators will be defined using each of the following criteria: LTOCS use; pre-visit exacerbation(s); asthma control status; and lung function [FEV₁% predicted] (12).

6. Statistical Analysis

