issues) had any impact on data quality. We will also explore the effects of the confounder COVID and adjust for this, if necessary. Therefore, we will investigate how trends differ before and after a given intervention using a single group interrupted time series analysis (ITSA) using calendar year as the time variable. This will involve creating a spline of year with a knot placed at either one or several intervention periods and creating a variable to partition time periods to before and after the given intervention. Where the key period differs for each country (e.g. introduction of QI initiatives as part of the ISAR), we will explore changes either side of the key period (set to be time zero). A linear mixed effects model will be used to assess the percentage of variables that are complete (objective 2) by intervention period and covariates, modelling variation in country as a random effect. The odds of LTOC use (objective 3) pre- and post-intervention period will use a logistic mixed effects model, also using a random intercept for each country. For both methods, 95% confidence intervals will be calculated using bootstrapping techniques. For the time-to-event components of objective 3 (i.e. time from LTOCS to stopping/reducing LTOCS) and objective 4 (i.e. time to initiating biologic by asthma severity indicator), we will use time-to-event analyses (both non-parametric and flexible parametric methods).

Objective 1: Proportion of patients in ISAR with 100% completeness of key research variables from 1 May 2017 to latest date available

We will use data from the ISAR registry from May 2017 to the latest date available to calculate the proportion of patients in each calendar year with 100% completeness of key research variables from 1 May 2017 to latest data available. Reviews will be stratified into KPRs and RRs, and method of provision for each country (i.e. ISAR-built electronic data capture vs bespoke). Joinpoint analysis will be used to identify each calendar year period (i.e. the predictor variable) at which there is a change in the proportion of patients reaching 100% completeness and the size of this change (percentage change in rate per calendar year). A log-linear model will be used to analyse percentage change in rate over time, reporting on the linear trend in each segment, also stratifying by country to explore country-specific effects. We will also investigate specific inflection points/periods during the observation period using ITSA.

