Objective 2: Completeness of recording of all core variables in ISAR

Annual trends and changes in the proportion of core variables will be investigated in ISAR, also stratifying by country and provision of data method. The completeness of individual core variables will also be investigated to assess the variables that are least likely to be complete.

We will use a combination of joinpoint regression (to investigate trends) and ITSA (to investigate pre-specified inflection time points) with variation in country modelled as a random effect for this component of the analysis, also stratifying by data capture method. **Appendix 1** (Section 13.1) shows the complete list of core variables in ISAR.

Objective 3: Differences in the proportion of patients in ISAR who are prescribed LTOCS varies over time, and the characteristics of these patients

Trends in the proportion of patients with a LTOCS prescription in a given year (i.e. yes/no) and average dose of LTOCS will be described and plotted by calendar year using a combination of joinpoint regression and ITSA to analyse significant changes in trends, also stratifying by country-specific data capture method. For those on LTOCS, we will also investigate the probability of stopping/reducing LTOCS dose (<5mg) using time-to-event analysis (non-parametric [Kaplan-Meier] and flexible parametric methods). Patient characteristics for people with and without missing/incomplete data on LTOCS will also be compared.

Objective 4: Trends in the severity of asthma indicators in those initiating biologic treatment over time

The probability of initiating biologic treatments by asthma severity indicator and calendar year will be investigated using time-to-event analyses (non-parametric and flexible parametric models).

7. Regulatory and Ethical Compliance

This study was designed and shall be implemented and reported in accordance with the criteria of the “European Network Centres for Pharmacoepidemiology and Pharmacovigilance (ENCePP)” and follows the ENCePP Code of Conduct (EMA 2014). Once a final version of the protocol has been agreed and reviewed by the advisory group, this study will be registered with ENCePP (www.encepp.eu).

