13.1. Appendix 1: Core variables in ISAR

The contract with each of the study countries and sites who contribute to the ISAR collaborative incorporates four schedules of data collection. Schedule 2 is the list of core variables, required at every visit. Schedule 4 contains a list of key research variables for key prior reviews, which incorporate first visits and those where a patient starts or switches biologic therapies. Schedule 5 is the list of key research variables for re-reviews (follow-up visits) and contains substantially fewer variables than the key prior reviews. Finally, schedule 6 contains variables for any information on key prior reviews before 2023 and does not include spirometry as this was introduced as a key variable in the 2023 Delphi exercise (including collaborators across each site/country). Information on baseline FeNO measurements was also included as a key research variable at baseline (i.e. key prior review) in the 2023 Delphi exercise. It was later dropped in a subsequent 2024 Delphi exercise.

All variables collected for the ISAR initiative, the schedule to which they contribute, and whether they are included as a core variable or as a key research variable at the ISAR patients' key prior review or re-review are shown in **Table A1**.

Table A1: All core variables collected for ISAR initiative, their inclusion in each data collection schedule, and their contribution to patients' key prior review and/or re-review as a key research variable

KEY VARIABLE STATUS	
	Both KPR and RR
	KPR only
	RR only

Core variable only

Category	Variable Field Name	Core variable	Key variable (KPR)	Key variable (RR)	Key/core variable by schedule number			
					2	4	5	6
Number of variables								
DOV	Date of visit							
AGE, GENDER, HEIGHT & WEIGHT	Date of Birth							
	Gender							
	Weight							
	Height							

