POST-BD-FVC	Post-bronchodilator FVC							
ALLERGEN TESTING	Was an Environmental Allergen Test conducted?							
	-Positive to perennial allergen (Serum Allergen Test)?							
	+Specify perennial allergen (Serum Allergen Test) (Select all that apply)							
	-Positive to perennial allergen (SPT)?							
	+Specify perennial allergen (SPT) (Select all that apply)							
ASTHMA CONTROL	Asthma Control							
TREATMENT PLAN	What is the current Clinical Management Plan? (Select all that apply)							
LTOCS AND DAILY DOSE	Is the patient prescribed Maintenance Oral Steroids?							
	Daily dose of Maintenance Oral Steroids							
LTOCS NAME AND START DATE	Maintenance Oral Steroid name							

	Start Date of Maintenance Oral Steroids							
PRESCRIPTION ICS+LABA/ICS/LABA/LAMA/THEO/LTRA	Is the patient on a prescription for ICS+LABA combination therapy?							
	Is the patient on a prescription for ICS (only)?							
	Is the patient on a prescription for LABA (only)?							

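### Objective 3(ii): Kaplan-Meier is named for time to stopping or reducing LTOCS, but on the listed variables the event is known only to lie between two visits of unspecified spacing

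*Protocol*

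**What the plan says.** Section 5 (Objective 3) plans to evaluate the proportion and "time to stopping/reducing the dose" in order to compare clinical practice over calendar time. Section 6.3 gives the time scale as "time from LTOCS to stopping/reducing LTOCS" and, on the method, states: "we will also investigate the probability of stopping/reducing LTOCS dose (<5mg) using time-to-event analysis (non-parametric [Kaplan-Meier] and flexible parametric methods".

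In section 13.1, the LTOCS items in Table A1 are "Is the patient prescribed Maintenance Oral Steroids", "Daily dose of Maintenance Oral Steroids", the steroid name and "Start Date of Maintenance Oral Steroids". Table 1 has only the first two. The text before Table A1 describes its content as "All variables collected for the ISAR initiative, the schedule to which they contribute"; the table's own title restricts it to core variables. Core variables are required at each visit.

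Section 4.2 sets the Objective 3 baseline at the first visit with LTOCS recorded as yes and excludes patients with only one visit. A re-review is defined only as a follow-up visit that is not a key prior review, with no interval given. The Objective 3 covariates are age, gender, country and country-specific factors. Visit-specific factors are listed for Objectives 1 and 2 but not here.

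**The concern.** Ordinary Kaplan-Meier needs an event time that is either known exactly or right-censored. With status and dose recorded at visits and no date for the change, all that is known is the last visit without the event and the first visit with it. If the detecting visit supplies the date, every event is recorded late, and later where visits are sparser. A flexible parametric model fitted to those dates as exact times has the same fault. The LTOCS start date does not help, because it does not locate the stop. Objective 4 is different, because biologic start dates are collected.

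The analysis is meant to show changes in practice. If visit spacing, or the completeness of visit entry, differed between calendar periods, countries or data-capture routes, part of any difference in the curves would reflect spacing and not prescribing. Nothing in the plan would reveal this.

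**Working it through.** The protocol gives no event count, median or visit interval for this analysis, so there is no stated figure to reproduce. The size was examined by simulation.

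**1. Inputs.** From the protocol: visit-level LTOCS status and dose, a visit-based baseline, no listed stop or dose-change date, and Kaplan-Meier as the named method. The feasibility table gives 72,796 / 20,293 = 3.6 re-reviews per new-patient visit. This does not fix the interval, because length of follow-up is not stated. Assumed, not in the protocol: constant hazard, visits every 3, 6 or 12 months with SD 25% of the interval, visit timing independent of the event, and a 60-month limit.

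**2. Truth.** Take a 12-month probability of 30%.
- Hazard = −ln(1 − 0.30)/12 = 0.0297 per month.
- Median = ln 2 / 0.0297 = 23.3 months.
- 24-month probability = 1 − 0.70² = 51.0%.

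**3. Visit-dated Kaplan-Meier.** There were 200,000 patients per setting. Each event was dated at the first visit after it occurred, and patients without an event were censored at their last visit.

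| Visits every | Median (months) | Delay (months) | Half interval (months) | 24-month probability |
|---|---|---|---|---|
| Truth | 23.3 | – | – | 51.0% |
| 3 months | 24.9 | 1.6 | 1.5 | 48.7% |
| 6 months | 26.5 | 3.2 | 3.0 | 46.2% |
| 12 months | 29.6 | 6.3 | 6.0 | 39.7% |

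The delay is close to half the interval in each row.

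**4. Effect on a comparison.** A second simulation used 20,000 patients per cell and true medians of 12, 18, 24 and 36 months. True stopping was identical across visit frequencies. With rates computed as events divided by visit-dated person-time, the spurious rate ratio for 6- versus 12-monthly visits was 1.18, 1.12, 1.09 and 1.07. For example, at a true median of 24 months the fitted medians were 26.3 and 28.6 months, and 28.6 / 26.3 = 1.09. For 3- versus 12-monthly visits the ratios were 1.29, 1.18, 1.14 and 1.09.

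**5. Same data, interval-censored likelihood.** Each event contributed S(last visit without it) − S(first visit with it). For visits every 3, 6 and 12 months the estimated medians were:
- true 12: 11.9 / 11.9 / 11.9
- true 18: 18.0 / 17.8 / 17.8
- true 24: 23.9 / 24.0 / 24.0
- true 36: 36.5 / 36.0 / 36.3

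Rate ratios between visit frequencies returned to 0.98–1.01. Because the simulation makes visit timing independent of the event, this shows what the method achieves when that assumption holds. It does not show that the assumption holds in the registry.

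**The case against.** **Table A1 may not be a full list.** A reader might infer that the registry holds no LTOCS stop date at all. The documents do not support that. The table's title says core variables, and Table 1 contains anti-TSLP prescription and start-date items that Table A1 lacks. The supportable statement is that no such date is listed. If one exists, the protocol should name it.

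**Event dating may be left to the analysis plan.** The protocol does not say that the event is dated at the detecting visit, and censoring detail often belongs in a later document. This stands in part. However, section 6.3 does name Kaplan-Meier, and the detecting visit is the only date the listed variables supply. That is a method fixed badly rather than a detail left out.

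**The comparative harm is not shown.** A reader might infer that the quality-improvement programme or a new eCRF will produce falsely faster stopping. The documents give no visit spacing for any country or year, so this cannot be asserted. Stratifying by country would also deal with stable spacing differences when practice is followed within a country. It would not deal with spacing that changes within a country over calendar time.

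**The size depends on where the curve is read.** At exactly 12 months, annual visits give 12.6% against a true 30%, and a reader might take that as the typical error. It is the worst reading point, because about half of the first follow-up visits have not yet taken place. At 36 months the figures for 3-, 6- and 12-monthly visits are 64.1%, 62.3% and 58.1%, against 1 − 0.70³ = 65.7%. The proportion with an observed event by 60 months is 82%, 82% and 80%, so the simple proportion stopped or reduced in Objective 3(ii) is much less affected.

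**The remedy has its own assumption.** Interval-censored methods require visit timing not to depend on the event. Patients who are tapering or more ill may be seen more often. This stands, and the plan should state the assumption.

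**Conclusion.** The concern holds for the time-to-event part of Objective 3(ii). On the listed variables the event is interval-censored, and the named Kaplan-Meier method would report stopping late by about half a visit interval. With an assumed true median of 23.3 months, that is 1.6, 3.2 and 6.3 months for visits every 3, 6 and 12 months. The direction was the same in every setting run. The sizes depend on assumed intervals, a constant hazard and visit timing independent of the event.

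Absolute times are delayed whatever the comparison. Differences between periods, countries or data-capture routes are biased only if spacing differs between them. The documents neither show nor exclude this, and the plan does not check it. The point is worth correcting before analysis; it does not undermine the other objectives.

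**What to change.** In section 6.3:

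- State whether a stop or dose-change date is recorded, and name it if so. Otherwise define the event as lying between the last visit without it and the first visit with it.
- Use a Turnbull estimate and an interval-censored likelihood for the parametric model as the main analysis. Keep visit-dated Kaplan-Meier as a sensitivity analysis.
- Report visit spacing by calendar period and country, and state the assumption that visit timing does not depend on the event.
- Reconcile the reduction cut-off, which is ≤5 mg in section 5 and <5 mg in section 6.3. The event must have one definition before its interval can be set.

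The cost is wording, modest programming and somewhat wider confidence intervals (the widening was not computed). No new data are needed.

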13.1. Appendix 1: Core variables in ISAR

The contract with each of the study countries and sites who contribute to the ISAR collaborative incorporates four schedules of data collection. Schedule 2 is the list of core variables, required at every visit. Schedule 4 contains a list of key research variables for key prior reviews, which incorporate first visits and those where a patient starts or switches biologic therapies. Schedule 5 is the list of key research variables for re-reviews (follow-up visits) and contains substantially fewer variables than the key prior reviews. Finally, schedule 6 contains variables for any information on key prior reviews before 2023 and does not include spirometry as this was introduced as a key variable in the 2023 Delphi exercise (including collaborators across each site/country). Information on baseline FeNO measurements was also included as a key research variable at baseline (i.e. key prior review) in the 2023 Delphi exercise. It was later dropped in a subsequent 2024 Delphi exercise.

All variables collected for the ISAR initiative, the schedule to which they contribute, and whether they are included as a core variable or as a key research variable at the ISAR patients' key prior review or re-review are shown in **Table A1**.

Table A1: All core variables collected for ISAR initiative, their inclusion in each data collection schedule, and their contribution to patients' key prior review and/or re-review as a key research variable

KEY VARIABLE STATUS	
	Both KPR and RR
	KPR only
	RR only

Core variable only

Category	Variable Field Name	Core variable	Key variable (KPR)	Key variable (RR)	Key/core variable by schedule number			
					2	4	5	6
Number of variables								
DOV	Date of visit							
AGE, GENDER, HEIGHT & WEIGHT	Date of Birth							
	Gender							
	Weight							
	Height							
ETHNICITY	Ethnicity							
OCCUPATION	What is the current occupation of the patient?							
SMOKING STATUS	What is the current smoking status of the patient?							
ASTHMA ONSET	At what age did the patient's asthma symptoms begin? Whole years or months if < 1 year							
OTHER FACTORS	Are there any other factors contributing to severe asthma symptoms?							
EXACERBATION	Number of exacerbations requiring rescue steroids in the past 12 months?							
INVASIVE VENTILATIONS	Total number of episodes of invasive ventilation ever?							
EMERG	Total number of A&E attendances for asthma in the past 12 months?							
HOSPITAL ADMISSION	Total number of hospital admissions for asthma in the past 12 months?							
ECZEMA	Indication of: Eczema							
ALLERGIC RHINITIS	Indication of: Allergic Rhinitis							
CHRONIC RHINOSINUSITIS	Indication of: Chronic Rhinosinusitis							
NASAL POLYPS	Indication of: Nasal Polyps							

OSTEOP	Does the patient have a diagnosis of Osteoporosis?							
OSTEOP_DTE	Diagnosis date for Osteoporosis							
T2DIAB	Does the patient have a diagnosis of Type II Diabetes							
T2DIAB_DTE	Diagnosis date for Type II Diabetes							
HIGHEST BLOOD OESINOPHIL COUNT	What is the Highest Blood Eosinophil Count (within the past year)?							
BEOS_DTE	Date of highest blood Eosinophil count (within the past year)							
BEOS_CNT	What is the Current Blood Eosinophil Count (latest)?							
IGE COUNT	What is the IgE Count (latest)							
PRE-BD-FEV1	Pre-bronchodilator FEV1							
POST-BD-FEV1	Post-bronchodilator FEV1							
PRE-BD-FVC	Pre-bronchodilator FVC							
POST-BD-FVC	Post-bronchodilator FVC							
ALLERGEN TESTING	Was an Environmental Allergen Test conducted?							
	-Positive to perennial allergen (Serum Allergen Test)?							
	+Specify perennial allergen (Serum Allergen Test) (Select all that apply)							
	-Positive to perennial allergen (SPT)?							
	+Specify perennial allergen (SPT) (Select all that apply)							
ASTHMA CONTROL	Asthma Control							
TREATMENT PLAN	What is the current Clinical Management Plan? (Select all that apply)							
LTOCS AND DAILY DOSE	Is the patient prescribed Maintenance Oral Steroids?							
	Daily dose of Maintenance Oral Steroids							
LTOCS NAME AND START DATE	Maintenance Oral Steroid name							

	Start Date of Maintenance Oral Steroids							
PRESCRIPTION ICS+LABA/ICS/LABA/LAMA/THEO/LTRA	Is the patient on a prescription for ICS+LABA combination therapy?							
	Is the patient on a prescription for ICS (only)?							
	Is the patient on a prescription for LABA (only)?							
	Is the patient on a prescription for LAMA?							
	Is the patient on a prescription for Theophyllines?							
	Is the patient on a prescription for Leukotrine Receptor Antagonist (LTRA)?							
	Is the patient on a prescription for Macrolide Antibiotic Treatment?							
ICS/LABA/LAMA/Theo/LTRA A start date	Start Date of ICS+LABA combination therapy?							
	Start Date of ICS?							
	Start Date of LABA?							
	Start Date of LAMA?							
	Start Date of Theophylline?							
	Start Date of Leukotrine Receptor Antagonist (LTRA)?							
	Start Date of Macrolide Antibiotic Treatment?							
ICS DAILY DOSE	ICS daily dose							
BIOLOGIC	Prescription for Anti-Interleukin 4 (Anti-IL4) Treatment?							
	Prescription for Anti-Interleukin 5 (Anti-IL5) Treatment?							
	Prescription for Anti-IgE Treatment?							
BIOLOGIC START DATE	Start Date of Anti-Interleukin 4 (Anti-IL4) Treatment?							
	Start Date of Anti-Interleukin 5 (Anti-IL5) Treatment?							

	Start Date of Anti-IgE Treatment?							
REASON FOR SWITCH	Reason for biologic switch							
ADHERENCE	Is there evidence of poor adherence?							
